## 9.2.2 Adverse Event Overview

An overview of TEAEs will be presented consisting of the number and percentage of subjects experiencing at least one event for each of the following AE categories:

- Any TEAE
- Any TEAE related to study drug according to the investigator
- Any TEAEs of Grade 3 or higher
- Any serious TEAE
- Any serious TEAE related to study drug according to the investigator
- Any TEAE leading to discontinuation of study drug
- TEAEs leading to interruption of study drug
- Any fatal TEAE
- AEs of special interest (AESI) (defined in Section [9.2.5](#))
- All deaths

## 9.2.3 Treatment-Emergent Adverse Events by SOC and/or PT

Treatment-emergent AEs will be summarized by SOC and PT; by maximum relationship to study drug as assessed by the investigator (e.g., reasonable possibility or no reasonable possibility) and SOC and PT; by maximum severity and SOC and PT; and by subject number and SOC and PT. Specific adverse events will be counted once for each subject for calculating percentages, unless stated otherwise. In addition, if the same adverse event occurs multiple times within a subject, the highest severity and level of relationship to investigational product will be reported.

If a subject has an AE with unknown severity or relationship to study drug, then the subject will be counted in the severity/relationship level category of "unknown" even if the subject has another occurrence of the same event with a severity present. The only exception is if the subject has another occurrence of the same AE with the highest level of severity or a relationship assessment of "Reasonable possibility." In this case, the subject will be counted under the most extreme severity/relationship category.

In addition, TEAEs will be summarized by PT and sorted by the overall descending frequency in the ABBV-3067 150 mg plus ABBV-2222 300 mg arm for Part 1 analysis and by the overall descending frequency in the ABBV-3067 150 mg plus ABBV-2222 fixed dose arm for Part 2 analysis.

#### **9.2.4 SAEs (Including Deaths) and Adverse Events Leading to Study Drug Discontinuation**

Treatment-emergent SAEs (including deaths) and AEs leading to study drug discontinuation will be summarized by SOC and PT and in listing format.

A listing of all deaths will be generated.

#### **9.2.5 Adverse Events of Special Interest**

The rash AESIs will be identified per a Product MedDRA Query (PMQ) of "Drug Induced rash (Cystic Fibrosis Transmembrane Regulator [CFTR] Modulators Product Specific)" and be summarized by SOC and PT. For rash related AESIs, the following categories will be summarized by treatment group:

- Any rash AESIs
- Any rash AESIs related to study drug according to the investigator
- Any rash AESIs leading to discontinuation of study drug
- Any rash AESIs leading to interruption of study drug
- Any serious rash AESIs
- Any serious rash AESIs related to study drug according to the investigator

Tabular listings of AESIs will also be provided.

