Hospitalization or Prolongation of Hospitalization	An event that results in an admission to the hospital for any length of time or prolongs the subject's hospital stay. This does not include an emergency room visit or admission to an outpatient facility.
Congenital Anomaly	An anomaly detected at or after birth, or any anomaly that results in fetal loss.
Persistent or Significant Disability/Incapacity	An event that results in a condition that substantially interferes with the activities of daily living of a study subject. Disability is not intended to include experiences of relatively minor medical significance such as headache, nausea, vomiting, diarrhea, influenza, and accidental trauma (e.g., sprained ankle).
Important Medical Event Requiring Medical or Surgical Intervention to Prevent Serious Outcome	An important medical event that may not be immediately life-threatening or result in death or hospitalization, but based on medical judgment may jeopardize the subject and may require medical or surgical intervention to prevent any of the outcomes listed above (i.e., death of subject, life threatening, hospitalization, prolongation of hospitalization, congenital anomaly, or persistent or significant disability/incapacity). Additionally, any elective or spontaneous abortion or stillbirth is considered an important medical event. Examples of such events include allergic bronchospasm requiring intensive treatment in an emergency room or at home, blood dyscrasias or convulsions that do not result in inpatient hospitalization, or the development of drug dependency or drug abuse.

All AEs reported from the time of study drug administration until 30 days or 5 half-lives after discontinuation of study drug administration will be collected, whether solicited or spontaneously reported by the subject. In addition, SAEs and protocol-related nonserious AEs will be collected from the time the subject signs the study-specific informed consent.

AbbVie will be responsible for suspected unexpected serious adverse reactions (SUSAR) reporting for the investigational medicinal product (IMP) in accordance with global and local requirements.

Adverse events will be monitored throughout the study to identify any of special interest that may indicate a trend or risk to subjects.

Adverse Events of Special Interest

Rash is an AE of special interest (AESI) and will be monitored during the study.

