In prior Phase 1 studies, there were isolated instances of nonserious generalized, maculopapular rash that occurred when ABBV-3067 and ABBV-2222 were administered together. The rashes resolved after study drug discontinuation. Maculopapular rash is a disorder characterized by the presence of macules (flat) and papules (elevated). Also known as morbilliform rash, maculopapular rash is one of the most common cutaneous AEs, frequently affecting the upper trunk, spreading centripetally, and associated with pruritus.

Rash is to be graded according to the CTCAE (adapted) version 5.0.³ All rash cases have to be reported within 24 hours from the time of knowledge of the event. Refer to the Operations Manual ([Appendix F](#)) for details about management of these events.

Adverse Event Severity and Relationship to Study Drug

The investigators will rate the severity of each AE according to the CTCAE version 5.0.³

Grading System for Adverse Events (a semicolon indicated "or" within the description of the grade)

Grade 1	Mild; asymptomatic or mild symptoms; clinical or diagnostic observations only; intervention not indicated
Grade 2	Moderate; minimal, local, or noninvasive intervention indicated; limiting age-appropriate instrumental ADL ^a
Grade 3	Severe or medically significant but not immediately life-threatening; hospitalization or prolongation of hospitalization indicated; disabling; limiting self-care ADL ^b
Grade 4	Life-threatening consequences; urgent intervention indicated
Grade 5	Death related to AE

ADL = Activities of Daily Living

- a. Instrumental ADL refer to preparing meals, shopping for groceries or clothes, using the telephone, managing money, etc.
- b. Self-care ADL refer to bathing, dressing and undressing, feeding self, using the toilet, taking medications, and not bedridden.

The investigator will use the following definitions to assess the relationship of the AE to the use of study drug:

Reasonable Possibility	After consideration of factors including timing of the event, biologic plausibility, clinical judgment, and potential alternative causes, there is sufficient evidence (information) to suggest a causal relationship.
No Reasonable Possibility	After consideration of factors including timing of the event, biologic plausibility, clinical judgment, and potential alternative causes, there is insufficient evidence (information) to suggest a causal relationship.

Pregnancy

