4.2 Recording Data and Analyses of Safety Findings

AEs will be coded using the Medical Dictionary for Regulatory Activities (MedDRA). The number and percentage of subjects with treatment-emergent adverse events (i.e., any event that begins or worsens in severity after initiation of study drug through 30 days post-study drug dosing) will be tabulated by primary MedDRA System Organ Class (SOC) and preferred term (PT). The tabulation of the number of subjects with treatment-emergent AEs by severity grade and relationship to study drug also will be provided. Subjects reporting more than 1 AE for a given MedDRA preferred term will be counted only once for that term using the most severe grade according to the severity grade table and the most related according to the relationship to study drug tables. Subjects reporting more than 1 type of AE within an SOC will be counted only once for that SOC.

Adverse Events of Special Interest

Isolated instances of nonserious, generalized, maculopapular rash have occurred in prior Phase 1 studies when ABBV-3067 and ABBV-2222 were administered together (see protocol Section 6.1). All rash AEs are considered adverse events of special interest (AESIs). These AEs have to be reported in real time (i.e., within 24 hours from the time of the knowledge of the event) using a study-specific rash questionnaire ([Appendix B](#)).

Maculopapular and other rash events are to be graded as follows (adapted from Common Terminology Criteria for Adverse Events [CTCAE] version 5.0):

- Grade 1** Macules/papules covering < 10% body surface area (BSA) with or without symptoms (e.g., pruritis, burning, tightness).
- Grade 2** Macules/papules covering 10% to 30% BSA with or without symptoms (e.g., pruritis, burning, tightness); or rash covering > 30% BSA with or without mild symptoms.
- Grade 3** Macules/papules covering > 30% BSA with moderate or severe symptoms.

Note: To calculate the percent of BSA, estimate the area covered by the actual macules/papules and do not include the clear skin between them. Imagine the rash coverage as if all of the macules and papules

coalesce into a single area. A diagram showing the contribution of different body parts to BSA, helpful to calculate % BSA, can be found at:

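### SAP 9.2.5 admits rash AESIs only through a product-specific MedDRA query of unstated coverage, although the protocol makes every rash AE an AESI

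*SAP*

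**What the plan says.** **Protocol and Operations Manual.** Protocol 6.1 names the event without qualification: "Rash is an AE of special interest (AESI) and will be monitored during the study". It adds that "All rash cases have to be reported within 24 hours from the time of knowledge of the event". Operations Manual 4.2 (Protocol Appendix F) states the scope outright: "All rash AEs are considered adverse events of special interest (AESIs"). These events are reported "using a study-specific rash questionnaire". The grading scale is not limited to one morphology: "Maculopapular and other rash events are to be graded as follows". The questionnaire itself (Operations Manual Appendix B) is headed by an AE serial number. It has tick boxes for many types of rash, including urticarial, vesicular, pustular, purpuric and exfoliating, and asks whether the investigator sees an alternative etiology.

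**SAP.** Section 9.2.5 gives one rule for the analysed set: "The rash AESIs will be identified per a Product MedDRA Query (PMQ"). The query's title and use are given as "Drug Induced rash (Cystic Fibrosis Transmembrane Regulator [CFTR] Modulators Product Specific)' and be summarized by SOC and PT". Six summary rows follow: any rash AESI, related, leading to discontinuation, leading to interruption, serious, and serious and related. Listings of AESIs are also planned. In the TEAE overview (SAP 9.2.2), the row "AEs of special interest (AESI) (defined in Section" points to 9.2.5, so it inherits the same rule.

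**The concern.** The two documents define the same set in different ways. The protocol defines it by what the site reports as rash. The SAP defines it by whether the coded term belongs to a query that it names but does not describe. The two sets coincide only if the query contains every term to which a reported rash may be coded. Nothing in the SAP shows that it does, and no planned step would reveal a difference.

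Rash is the only AESI named in Protocol 6.1 and the only risk described in detail in Protocol 2.2. Safety and tolerability are among the stated grounds for choosing the ABBV-2222 dose for Part 2 (Protocol 3.1). With arms of 9 or 18, a count that is short by one subject visibly changes the rate that a reader of the AESI table sees.

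**Working it through.** The plan states no figure on this point, so there is none to reproduce. The check is a comparison of texts, followed by the scale of a single miss.

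**1. Set that the protocol collects.** All rash AEs, of any cause or morphology (Protocol 6.1; Operations Manual 4.2), each with a questionnaire carrying the AE serial number (Operations Manual Appendix B).

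**2. Set that the SAP analyses as AESIs.** AEs whose coded term is in the named query (SAP 9.2.5). The questionnaire is not used as a source, no term list or version is attached, and no reconciliation is described.

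**3. Outputs that depend on the SAP's set.** The six rows and the listings in 9.2.5, and the AESI row in 9.2.2.

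**4. Where a rash outside the query would still appear.** In the TEAE tables by SOC and PT, by maximum relationship and by maximum severity (SAP 9.2.3). If serious or leading to discontinuation, it would also appear in the tables and listings of SAP 9.2.4. These count within SOC or PT. No planned table outside 9.2.5 counts subjects with any rash across preferred terms.

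**5. Scale of one missed subject.** Change in rate = 1 / n, with planned arm sizes from Protocol 4.1:
- n = 9: 1/9 = 11.1 percentage points
- n = 18: 1/18 = 5.6 percentage points
- combined placebo, 18 + 9 = 27: 1/27 = 3.7 percentage points

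**6. Chance of at least one miss (illustration only).** Let s be the probability that the query captures a subject with reported rash, and let k such subjects be independent. The chance that at least one is missing is 1 − s^k. The documents give neither s nor k, so the values below are assumptions:

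| Assumed s | k = 5 | k = 10 |
|---|---|---|
| 1.00 | 0% | 0% |
| 0.95 | 23% | 40% |
| 0.90 | 41% | 65% |
| 0.80 | 67% | 89% |

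The table shows only that modest gaps in a query would matter at plausible event counts. It is not evidence that this query has gaps.

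**The case against.** The strongest reply is that no loss has been shown. The term list is not in the documents, and if it covers every rash term nothing is missed. That is correct.

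A reader might also infer from the query's title that it keeps only rashes judged to be drug-induced. The documents do not support that. A MedDRA query selects by coded term, not by judged cause, and 9.2.5 has one row for any rash AESI and a separate row for those the investigator considers related, so unrelated rashes are expected in the set. The title suggests a narrower scope than all rash AEs but does not prove it.

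Nor would a missed rash vanish from safety review. It stays in the general TEAE tables, and in the SAE or discontinuation tables where those apply. Sites report all rash cases within 24 hours, and the DMC reviews unblinded safety data under its own specifications. In small arms, listings can be read case by case. This limits the consequence to the AESI outputs. It does not replace a correct subject-level count of any rash, because the general tables count by preferred term and the AESI listings draw on the same section's definition.

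On severity, maximum severity by SOC and PT is already planned (SAP 9.2.3). Operations Manual 4.2 links Grade 3 rash to discontinuation of study drug, so the discontinuation row should contain Grade 3 rashes that are in the query. The absence of a rash-grade row contradicts nothing in the protocol; adding one is optional.

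**Conclusion.** The point holds in conditional form. SAP 9.2.5 does not ensure that the analysed rash AESIs are the protocol's rash AESIs, and it has no check that would expose a difference. A reported rash coded outside the query would be absent from the AESI tables and the overview row, and present elsewhere. The number of such events is unknown and may be zero. Each affected subject lowers the AESI rate by 5.6 points in an arm of 18 or 11.1 points in an arm of 9, taking the planned arm sizes as achieved.

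Two stronger readings are tempting but unsupported. One is that the two sets are known to differ; without the term list this cannot be said. The other is that the rash count is the main safety input to dose selection. Protocol 3.1 and 4.1 list safety with efficacy and pharmacokinetics, and neither section gives rash a weight, rule or threshold.

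**What to change.** In SAP 9.2.5:

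1. Define rash AESIs as all AEs that are hits of the named query **or** have a rash questionnaire, linked by the AE serial number on the questionnaire. The documents describe no separate investigator AESI flag, so the questionnaire is the field to use.
2. Cite the query's term list and version, alongside the MedDRA version that SAP 9.2 already says will be recorded.
3. Before each database lock, list the events found by one route but not the other, and review them blinded to treatment.
4. Optionally, add a row for each subject's maximum rash grade on the adapted CTCAE scale of Operations Manual 4.2, taken across preferred terms.

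The overview row in 9.2.2 then follows without further change.

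**Cost.** SAP wording, one merge of existing data and a short blinded review before each lock. No new data or visits are needed. The count may include some rashes not thought to be drug-induced. The protocol already counts these as AESIs, and the existing relatedness row separates them. A rash with neither a query hit nor a questionnaire would still be missed, but only if the site had not followed the reporting requirement.

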### **9.3 Analysis of Laboratory Data**

Data collected from central and local laboratories, including additional laboratory testing due to an SAE, will be used in all analyses, except for Baseline where SAE-related laboratory assessments on or before the first dose of study drug will be excluded. The

clinical laboratory tests defined in the protocol operations manual (e.g., hematology and clinical chemistry) will be summarized.

Each laboratory variable will be summarized for all visits (starting with Baseline) with the number of non-missing observations, mean and standard deviation, median, minimum and maximum. Mean change from baseline to each applicable post-baseline visit will be summarized for laboratory variables with the number of observations, baseline mean, and visit mean. The change from baseline mean, standard error, and 95% confidence interval will be presented for the mean change from baseline within each treatment group.

In the DB Treatment Period, changes in selected laboratory parameters will be tabulated using shift tables for categories of low, normal, or high based on the normal ranges. A shift table from Baseline values of high or normal to post-Baseline low, or from Baseline values of low or normal to post-Baseline high will be created based on the worst post-Baseline value during treatment. Shifts from Baseline grade to the worst post-Baseline grade (CTCAE 4.03) during treatment will be summarized in a cross-tabulation of grades. Similar shift tables by normal range and grade will be provided for shifts from baseline to the final post-Baseline value.

Laboratory abnormalities for selected parameters will be evaluated based on Potentially Clinically Significant (PCS) criteria ([Appendix B](#)). For each laboratory PCS criterion, the number and percentage of subjects who have a laboratory value meeting the criteria during treatment will be summarized. A post-baseline value must be more extreme than the baseline value to be considered a PCS finding. Listings will be provided to summarize subject-level laboratory data for subjects meeting PCS criteria.

The number and percentage of subjects with laboratory values meeting the following criteria during treatment will be summarized to support the assessment of potential hepatotoxicity.

- ALT > 3 × ULN, > 5 × ULN, > 10 × ULN, > 20 × ULN
- AST > 3 × ULN, > 5 × ULN, > 10 × ULN, > 20 × ULN

- TBL > 1.5 × ULN, > 2 × ULN
- ALT and/or AST > 3 × ULN and TBL > 1.5 × ULN
- ALT and/or AST > 3 × ULN and TBL > 2 × ULN
- ALT > 3 × ULN and TBL > 1.5 × ULN
- ALT > 3 × ULN and TBL > 2 × ULN
- Alkaline phosphatase > 1.5 × ULN

Listing of ALT, AST, total bilirubin, and alkaline phosphatase values will be provided for each subject who met one or more of the criteria defined above.

An Evaluation of Drug Induced Serious Hepatotoxicity (eDISH) plot displaying the maximum on-treatment values of total bilirubin (as multiple of ULN) versus ALT (as multiple of ULN), not necessarily concurrent, will be created. A similar eDISH plot and subject listing will be presented for AST vs. total bilirubin.

#### **9.4 Analysis of Vital Signs**

Vital sign measurements include systolic blood pressure [mmHg], diastolic blood pressure [mmHg], pulse [beats per minute], body temperature [°C], oxygen saturation [%], respiratory rate [breaths/minute] and weight [kg].

Each vital sign variable will be summarized for all visits (starting with Baseline) with the number of non-missing observations, mean and standard deviation, median, minimum and maximum. Mean change from baseline to each applicable post-baseline visit will be summarized for each vital sign variable, with the number of observations, baseline mean, and visit mean.

Vital sign variables will be evaluated based on potentially clinically important (PCS) criteria ([Appendix B](#)). For each vital sign PCS criterion, the number and percentage of subjects who have a vital sign value meeting the criteria during treatment will be summarized. A post-baseline value must be more extreme than the baseline value to be

considered a PCS finding. Listings will be provided to summarize subject-level vital sign data for subjects meeting PCS criteria.

## **9.5 Safety Subgroup Analyses**

There are no safety subgroup analyses planned for this study.

## **9.6 Other Safety Analyses**

### **Pulse Oximetry**

For oxygen saturation values by pulse oximetry, a summary of observed values and change from baseline values will be provided at each visit by treatment group. The number and percentage of subjects with shift changes from baseline (categorized as  $< 95\%$  or  $\geq 95\%$ ) to the minimum value of oxygen saturation during treatment (categorized as  $< 90\%$ ,  $90 - < 95\%$ , or  $\geq 95\%$ ) will be tabulated by treatment group.

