4 INVESTIGATIONAL PLAN

4.1 Overall Study Design and Plan

This is a multicenter, multi-country, Phase 2, double-blind, placebo-controlled, parallel-arm, 2-part study of ABBV-3067 given alone and in combination with ABBV-2222 for 28 days in adult subjects with CF who are homozygous for F508del CFTR mutation. This study is designed to evaluate the safety and efficacy of ABBV-3067 alone and in combination with ABBV-2222, and in a sequential manner that will also allow dose selection for these compounds.

This study will enroll subjects with a confirmed clinical diagnosis of CF who are homozygous for the F508del CFTR mutation. In both Part 1 and Part 2, randomization will be stratified by ppFEV₁ at Screening (< 70% vs ≥ 70%). See Section 5 for detailed information regarding eligibility criteria.

Study drug will be administered in the morning from Day 1 to the day before the Day 29 visit. In Part 1 of the study, a fixed 150 mg once daily (QD) dose of ABBV-3067 will be administered with ABBV-2222 in a dose range-finding manner to enable a dose selection for ABBV-2222 for Part 2 and future combination studies. In addition, ABBV-3067 will be given alone (i.e., with placebo for ABBV-2222) to evaluate the safety and efficacy of ABBV-3067 at 2 dose levels. Differences in endpoint values between the dual therapy arms and monotherapy arms, from this study and a previous Phase 2 study (Study GLPG2222-CL-202), will demonstrate the respective contributions of ABBV-3067 and ABBV-2222 to the combination.

In Part 2 of the study, the dose of ABBV-2222 selected from Part 1 will be administered with ABBV-3067 in a dose-ranging manner to enable selection of the ABBV-3067 dose for future combination studies.

Part 1

ABBV-3067 will be given alone or in combination with different dose levels of ABBV-2222 for 28 days. CF subjects (approximately n = 117) will be randomized to 8 parallel treatment arms with regimens defined below. The randomization ratio will be 1:1:1:2:2:2:2:2 for Regimens A through H in Part 1.

Regimen	ABBV-3067	ABBV-2222	Number of Subjects
A	50 mg	Placebo	9
B	150 mg	Placebo	9
C	150 mg	10 mg	9
D	150 mg	30 mg	18
E	150 mg	100 mg	18
F	150 mg	200 mg	18
G	150 mg	300 mg	18
H	Placebo	Placebo	18

Part 2

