- ✓ 9. ppFEV₁ ≥ 40% and ≤ 90% of predicted normal for age, gender, and height (Global Lung Function Initiative [GLI] equations) at Screening
- ✓ 10. SwCl at the Screening visit must be ≥ 60 mmol/L. For subjects who participated in Study M19-771, it is acceptable to use the SwCl value that the central lab provided from the screening visit in Study M19-771 to establish eligibility.

Subject History

- ✓ 11. Stable pulmonary status, i.e., no respiratory infections or exacerbations requiring a change in therapy (including antimicrobials) or causing an acute decline in ppFEV₁ of > 10% from usual baseline within 4 weeks prior to Day 1 (first dose of study drug).
- ✓ 12. Absence of comorbidities and medical history items listed below, or others that, in the opinion of the investigator, may pose additional risk by participating in the study, or may confound the results of the study.
 - a. Cirrhosis with portal hypertension (e.g., splenomegaly, esophageal varices)
 - b. Past or present positive sputum culture for organisms that are often associated with a faster decline in pulmonary status (e.g., *Mycobacterium abscessus*, *Burkholderia cenocepacia* or *B. dolosa*, *Aspergillus fumigatus* infection or allergic bronchopulmonary aspergillosis [ABPA]) is allowed if, in the opinion of the investigator, clinical stability has not been adversely affected. Subjects with these organisms can remain on chronic treatment for them if applicable, as long as the medications are not prohibited in this study (e.g., clarithromycin, rifampin, itraconazole, see table in Section 5.3). To assure clinical stability, treatment for these organisms should start at least 8 weeks prior to screening, and the subjects will be expected to continue the treatment through the final study visit.
 - c. History of malignancy within past 5 years (except for excised basal cell carcinoma of the skin with no recurrence, or treated carcinoma in situ of the cervix with no recurrence)
 - d. Abuse of alcohol, medications, or illicit drugs within 1 year prior to Screening, per the investigator.
 - e. Smoking or vaping tobacco or cannabis products within 1 year prior to Screening.
 - f. History of solid organ or hematopoietic transplantation.
 - g. History of known sensitivity to any component of the study drug.
 - h. Need for supplemental oxygen while awake, or > 2 L/minute while sleeping.

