## **8.0 Efficacy Analyses**

### **8.1 General Considerations**

All efficacy analyses will be conducted for the FAS. All tests will be 2-sided at an alpha level of 0.05. For each part of the study, the efficacy analysis will be performed after all ongoing subjects have completed the study part and the database has been locked.

For the primary efficacy endpoint, the null hypothesis that the within-group absolute change from baseline in ppFEV1 through Day 29 is zero will be tested for each treated group at 2-sided alpha of 0.05.

Unless otherwise specified, any subject who is randomized based on a wrong stratum will be analyzed according to the actual stratum to which the subject belongs.

"Baseline" refers to the last non-missing observation before the first administration of study drug.

Unless otherwise specified, continuous variables will be analyzed using Mixed-Effect Model Repeat Measurement (MMRM) method with the model based mean and standard error being provided. The Baseline and visit means will also be presented for each treatment group among subjects who have both Baseline and at least one post Baseline visit values. Treatment groups will be compared using MMRM model as described in Section 8.2. Point estimates and 95% CIs of mean change from Baseline within each treatment group, the difference between each active treatment group and placebo, and the difference between each combination therapy arm and the ABBV-3067 150 mg monotherapy arm (Part 1 only) will be provided. Note that both placebo arms in Part 1 and Part 2 will be combined into one placebo group for the Part 2 model comparison.

Plots of the primary endpoint and certain secondary endpoints by treatment group will be used to visualize the change of endpoint values over time and the difference between treatment groups.

Use of bronchodilator medications and/or airway clearance techniques may affect lung function measurements in the short term. Therefore, post-baseline spirometric measurement that are collected inconsistently with the conditions for the baseline spirometric measurement will be excluded from the efficacy analysis. For example, if baseline spirometric measurement was collected prior to bronchodilator use, then any spirometric measurement collected post bronchodilator use at a subsequent visit will be excluded from analysis.

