**Table B-3. Criteria for Potentially Clinically Important Vital Sign Values**

Vital Sign	Category	Criteria for Potential Clinically Significant Vital Signs	Reference
Systolic blood pressure	Low	Value $\leq$ 90 mmHg and decrease $\geq$ 20 mmHg from Baseline	Vaccine Trial Guidance, Grade 1 or above
	High	Value $\geq$ 160 mmHg and increase $\geq$ 20 mmHg from Baseline	CTCAE, Grade 3 or above, 2018 ESC/ESH guidelines
Diastolic blood pressure	Low	Value $\leq$ 50 mmHg and decrease $\geq$ 10 mmHg from Baseline	
	High	Value $\geq$ 100 mmHg and increase $\geq$ 10 mmHg from Baseline	CTCAE, Grade 3 or above, 2018 ESC/ESH guidelines
Pulse	Low	Value < 50 bpm and decrease $\geq$ 15 bpm from Baseline	Vaccine Trial Guidance, Grade 2 or above
	High	Value $\geq$ 116 bpm and increase $\geq$ 15 bpm from Baseline	Vaccine Trial Guidance, Grade 2 or above
Weight	Low	$\geq$ 5% decrease from baseline	CTCAE, Grade 1 or above
	High	$\geq$ 10% increase from baseline	CTCAE, Grade 2 or above
Temperature	High	> 39.0	CTCAE, Grade 2 or above
Oxygen saturation	Low	< 90%	

ESC = European Society of Cardiology; ESH = European Society of Hypertension

Note: A post-baseline value must be more extreme than the baseline value to be considered a potentially clinically significant finding.

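### The oxygen-saturation shift table in SAP 9.6 has no <90% band at baseline, so its <95%-to-<90% cell mixes new falls below 90% with subjects who were already there

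*SAP*

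**What the plan says.** SAP 9.6 (Pulse Oximetry) plans two things: "a summary of observed values and change from baseline values will be provided at each visit by treatment group", and a table of shifts from baseline "to the minimum value of oxygen saturation during treatment". In the shift table, baseline is classed as <95% or ≥95%, and the minimum as <90%, 90-<95% or ≥95%. Section 9.6 does not require the on-treatment value to be worse than baseline. SAP 8.1 says that baseline "refers to the last non-missing observation before the first administration of study drug".

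Saturation is also a vital sign under SAP 9.4. Table B-3 sets its PCS limit at <90%, with the condition "A post-baseline value must be more extreme than the baseline value to be considered a potentially clinically significant finding". SAP 9.4 adds subject-level listings for subjects who meet a PCS criterion.

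The eligibility criteria (Protocol 5.1) set no minimum saturation. The nearest limit, under criterion 12, is "Need for supplemental oxygen while awake, or > 2 L/minute while sleeping".

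**The concern.** A shift table separates change from no change only if the band of interest exists on both axes. Here the lowest band exists only on treatment. Eligibility does not rule out a baseline below 90%, so a subject who starts at 88% and stays at 88% is counted in the same cell as one who falls from 94% to 88%.

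At stake is how one descriptive safety table reads. SAP 9.1 presents safety by arm, and safety data feed the dose choices in Protocol 3.1. Most arms hold 9 or 18 subjects, so a single subject whose status is unclear is visible in the percentages. The shift table and the PCS table can also give different <90% counts for the same arm without explanation.

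**Working it through.** **Inputs.** Shift-table bands: SAP 9.6. PCS rule (<90% and lower than baseline): SAP 9.4 and Table B-3. Arm sizes of 9 and 18: Protocol 4.1. Total of 189: Protocol Synopsis. On-treatment oximetry at Day 15 and Day 29: Protocol Appendix D. The plan states no figure to reproduce.

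**Step 1: classify example pairs** (baseline, then on-treatment minimum; the values are illustrations).

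| Pair | SAP 9.6 cell | Same three bands on both axes | PCS? |
|---|---|---|---|
| 88, 88 | <95 to <90 | <90 to <90 | no |
| 88, 89 | <95 to <90 | <90 to <90 | no |
| 88, 87 | <95 to <90 | <90 to <90 | yes |
| 94, 88 | <95 to <90 | 90-<95 to <90 | yes |
| 97, 88 | ≥95 to <90 | ≥95 to <90 | yes |
| 88, 91 | <95 to 90-<95 | <90 to 90-<95 | no |

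The first four pairs share one SAP cell, although only the fourth is a new fall below 90%. The PCS rule removes the first two but keeps the third. The pair 89, 88 behaves like the third.

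**Step 2: what the planned outputs say about new falls** (baseline ≥90%, minimum <90%). Every new fall has a minimum below both 90% and baseline, so it is a PCS finding. Every subject in the ≥95-to-<90 cell is a new fall. If both tables use the same readings, then:

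count in ≥95-to-<90 cell ≤ new falls ≤ PCS count.

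The planned tables bracket the count. The PCS listings would allow it to be fixed by hand.

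**Step 3: how many subjects.** The documents give no saturation distribution, so these are assumptions: true values normal with mean 95 or 96 and between-subject SD 2 or 2.5; within-subject SD 1; readings rounded to 1% and capped at 100; minimum of two on-treatment readings; no drug effect.

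A baseline reading rounds to below 90 with probability Φ((89.5 − mean)/√(SD² + 1²)).

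- Mean 96, SD 2: Φ(−6.5/2.24) = 0.002; × 189 = 0.3 subjects.
- Mean 95, SD 2.5: Φ(−5.5/2.69) = 0.020; × 189 = 3.9 subjects.
- With a smaller SD of 1.5 at mean 95: Φ(−5.5/1.80) = 0.0011; × 189 = 0.2 subjects.

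Simulation of 2 million subjects per setting, over the four settings with means 95-96 and SDs 2-2.5, gives:

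- Below 90% both at baseline and on treatment: 0.1-2.6 of 189. At the upper end, 2.6 × 18/189 = 0.25 per 18-subject arm and 2.6 × 9/189 = 0.12 per 9-subject arm.
- In the affected cell with a minimum not lower than baseline: 0.1-1.7 of 189.
- Share of the <95-to-<90 cell already below 90% at baseline: 24-45%.
- Share of PCS findings already below 90% at baseline: 8-23%.

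**Step 4: weight of one subject.** 1/9 = 11.1%, 1/18 = 5.6%, and 1/27 = 3.7% in the combined placebo group (18 + 9). This is the weight of any single subject, not an effect of the banding.

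**The case against.** The strongest reply is that the rest of the plan already covers most of this. The PCS table works at the same 90% threshold, is shown by arm, and excludes the most misleading cases, those unchanged or improved. Its listings let a reader see whether a value below 90% was new. The expected number of affected subjects is well under one per arm, and no test, stopping rule or explicit dose-selection threshold uses this cell. All of that stands, and it keeps the point minor.

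It does not remove the point. The PCS count still includes subjects who were below 90% and slipped further, the summaries by visit are at group level, and a listing is not a tabulated count.

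Stronger readings are tempting, but the documents do not support them:

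- *Every subject below 90% at baseline is tabulated as a shift to <90%.* No. A subject who goes from 88% to a minimum of 91% falls in the 90-<95% column.
- *The table cannot show new desaturation at all.* No. The ≥95%-to-<90% cell holds only new falls.
- *A contaminated cell would look like a drug effect.* The row is labelled <95%, so it claims no normal baseline. Such subjects can occur in any randomised arm, and a combined placebo column is shown.
- *A quarter to nearly half of the cell is wrong, so the problem is large.* That share belongs to a very small cell and rests wholly on assumed saturation values.

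**Conclusion.** The mismatch between the bands is in the text of SAP 9.6, and its consequence follows by classification alone: the <95%-to-<90% cell combines falls from 90-94% with subjects below 90% at both times. No planned table gives the complete by-arm count of new falls below 90%, although the listings allow it to be rebuilt. The likely size is small, about 0.1-2.6 of 189 subjects below 90% both at baseline and on treatment. That figure depends on the assumed means, SDs and absence of drug effect, and would be smaller with a narrower spread. The efficacy analyses are untouched. This is a minor point of presentation, worth correcting because the correction is free.

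**What to change.** In SAP 9.6, class both baseline and the on-treatment minimum as <90%, 90-<95% and ≥95%. Add one summary row by arm: subjects with baseline ≥90% and on-treatment minimum <90%. The pairs 88, 88 and 94, 88 then fall in different cells, and the row supplies the missing count directly.

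The cost is one changed phrase and one extra table row. Oximetry is already collected at Screening, Day 1, Day 15 and Day 29, so no new data, visit or protocol amendment is needed.
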